2. To assess the safety of extending the interval of INR follow-up in patients.

Hypothesis: We hypothesize that there will not be a difference between the bleeding and thromboembolic events from baseline (12 months prior to study enrollment) to events/year at 6, 12, and 24 months.

Hypothesis: We hypothesize that there will not be a difference in the patient's time in therapeutic range (TTR) from baseline (12 months prior to study enrollment) compared to the TTR at 12 and 24 months.

3. To examine patients' and providers' acceptance of the intervention (to extend the follow-up interval of INR monitoring).

Hypothesis: We hypothesize that both patients and providers will favorably view the intervention.

Background:

Anticoagulation treatment with vitamin K antagonists, such as warfarin, can be complicated by many variables, such as drug interactions, diet, health status, other medications, and adherence. Frequent INR monitoring is required to keep patients' INR values within their target therapeutic range to lower the risk of hemorrhagic or thrombotic adverse events. However, some patients remain on the same warfarin dose with INRs within their goal range for extended periods of time. Predictors of very stable INR control for patients on long-term anticoagulation with warfarin include age greater than 70 years, male gender, INR target less than 3.0, and absence of heart failure, diabetes, or other chronic diseases.^{1, 2}

The most recent American College of Chest Physicians 2012 guidelines recommend an INR testing frequency of up to 12 weeks over 4 weeks in patients on warfarin with consistently stable INRs (Grade 2B; weak recommendation, moderate-quality evidence).³ The guidelines define stable INRs as at least 3 months of INRs that are within therapeutic range, thus not requiring changes in warfarin dose. These guidelines are now more comparable to those from the United Kingdom, where the practice of a 12-week INR monitoring interval has been usual practice.⁴ Despite the guideline recommendations, many United States anticoagulation providers are hesitant to extend the duration of INR follow-up to 12 weeks, as historically, the recommended interval and standard clinical practice for INR follow-up was a maximum of 4-6 weeks.

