within goal INR range for 6 or 12 months, to other patients, defined as one or more INRs outside of goal range during a 6 or 12 month period.^{1,2} Both studies found that bleeding and thromboembolic events were significantly lower with stable patients compared to the other patients on warfarin. Schulman et al. found no difference between the 4-week and 12-week groups in regards to major bleeding events, objectively verified thromboembolic events, and death.¹⁰ Schulman defined bleeding events per previously published criteria.¹¹ Although the Schulman et al study demonstrated favorable results, it is unknown if the patient contact every 4 weeks contributed to the positive outcomes. Additionally, the anticoagulation population in a VA Anticoagulation Clinic may be different (increased age, more comorbidities). Thus, we propose to examine an extended interval of INR follow-up in eligible patients at the William S. Middleton Memorial Veterans Hospital.

The Anticoagulation Clinic at the William S. Middleton Memorial Veterans Hospital and its associated community-based outpatient clinics is a pharmacist-managed service. The clinic currently follows approximately 1800 unique patients. The clinic manages the initiation of antithrombotic therapy, follows patients on short-term and long-term antithrombotic therapy, manages the transition from inpatient to outpatient care, and coordinates warfarin interruptions for procedures using low-molecular weight heparin if warranted. During an initial visit to the clinic, patients are oriented to warfarin as well as clinic procedures. A patient and provider responsibilities document is reviewed with all patients. For subsequent visits and INR assessments, patients are either seen in clinic or receive follow-up by telephone. The maximum interval between INRs is currently 5-6 weeks. Pharmacists have prescriptive authority under a scope of practice. This type of clinic is similar to other anticoagulation clinics in the Veteran Affairs system nationally and is considered high-quality anticoagulation management.¹²

Methods and Procedures

Design:

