The events rates for 2013 clinic data are listed below, including a 95%CI. Additionally, ranges for event rates over the past 4 years are included.

- Major bleed: 1.88% (95%CI 1.3-2.62%); range of 1.8-2%
- Serious bleed: 0.5% (95%CI 0.23-0.94%); range of 0-0.5%
- Thromboembolism: 0.22% (95%CI 0.06-0.6%); range of 0.2-0.44%

Stoppage rules for the study:

1. Stoppage rules for the study (based on event rates from the Schulman, et al. article) are included below. If the study is stopped early, all subjects will be scheduled for an INR within 6 weeks of their last INR, which is usual practice for the clinic.

Data from Schluman study				Madison VA	
Event	# from Schulman study	Rate per 1 year	95%CI of the 1 year rate from Schulman	Approx Count Based on 50 patients enrolled using upper end of 95% CI	Stoppage of Study
TE (includes TE-related death)	4	1.6%	0.4-4	2	3
Composite of TE, TIA, and major bleeding, TE-related death	12	4.8%	2.5-8.2	4.1	5

2. If an event occurs:
 - a. The PI or one of the Co-PIs will thoroughly evaluate the event to determine if it was related to study participation. . The following chart will be used to determine if the event was related to study participation.

Bleeding or TE event [‡]	On Extended Interval at Time of Event or within 6 Weeks of Event	INR Measure at visit following extended interval and/OR at Time of Event	Relationship to Hemostasis (as relates to INR direction/ magnitude)	Level of Attribution
Yes	Yes	Within target range	-	Possible
Yes	Yes	Outside target range	No relationship or uncertainty	Possible
Yes	Yes	Outside target range	Possible relationship	Probable
Yes	Yes	Outside target range	Definite relationship	Definite*

*Stopping rules apply to the events with a definite attribution. (Additional events may apply based on the discretion of the DMC and IRB.)

[‡] If the event was due to accident, injury, or other clear cause, attribution may not follow table.

- b. If a patient has a major bleeding or thromboembolic event, our protocol states that the patient will return to usual care and must be on the same dose for 6 months until they are able to requalify for the extended INR interval.

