Adverse events (AEs) collected for this study only include bleeding and thromboembolic events. Serious adverse events (SAEs) will be documented per VA and IRB definitions. AEs will be entered into OnCore after the retrospective review of the medical record at 6, 12, and 24 months after participant enrollment in the study. SAEs are entered into the SAE documentation area in OnCore as they occur, which may not align with the time period for the chart review. The SAEs that include bleeding or thromboembolism will be entered in real-time to the AE table in OnCore.

Measures: The outcomes of this study include feasibility, safety, and acceptability of extending the interval of INR follow-up to 12 weeks in stable warfarin patients. We propose to use the following measures:

1. Feasibility: We will examine the following:
 - a. Rates of participant accrual (patient interest in participating and reasons for not participating). Number of withdrawals and reasons for withdrawal from protocol or study.
 - b. Change in frequency of appointments from baseline
 - c. Frequency and type of protocol deviations from both participants and study staff
 - d. Frequency of time outside of extended INR interval protocol and why
 - e. Knowledge assessment of study staff regarding study protocol
2. Safety: We will examine the following:
 - a. Participant reported and EMR review of bleeding events. Study participant bleeding events for 12 months prior to enrollment and during the study will be compared to the clinic's bleeding event rate. The following definitions will be used to categorize bleeding:
 - i. Major
 1. Fatal or symptomatic bleed into a critical area or organ
 2. Bleeding leading to hospitalization
 3. Transfusion of 2 units or more PRBCs
 - ii. Serious
 1. Bleeding leading to ED or UC visit or additional testing
 - b. Participant reported and EMR review of thromboembolic events that are objectively verified. Study participant thromboembolic events for 12 months prior to study enrollment and during the study will be compared to the clinic's thromboembolic event rate.
 - c. Participant reported and EMR review of healthcare utilization: hospitalizations, ED visits, urgent office visits, telephone triage related to anticoagulation. Utilization for 12 months prior to study enrollment will be compared to utilization during study enrollment.
 - d. Baseline TTR (12 months prior and 6 months prior) for each patient and during study¹⁴
 - e. Number of extreme INRs (<1.5, ≥4.5)

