Sample Size: As this is a feasibility study, the primary concerns are whether or not this process could be incorporated into the normal anticoagulation clinic procedures and workflow. Results from this study can be utilized for calculating sample size and power statistical tests in future larger studies.

Analysis:

Accrual rate will be determined by average participants enrolled per week. Dropout rate will be determined by the number of participants lost to follow up out of the total number of participants

enrolled. Descriptive statistics (percentages, means, rates, and standard deviations) will be determined for all recorded baseline variables. Differences from baseline and at study completion will be compared utilizing McNemar Test for categorical data and paired t-test or Wilcoxon Signed-Rank Test for continuous and ordinal data (respectively). Thematic analysis will be utilized for to determine themes of satisfaction and/or concerns and barriers regarding the extended follow-up protocol from of the focus groups.

References

4. Guidelines on oral anticoagulation: third edition. *Br J Haematol*. May 1998;101(2):374-387.

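### Measures 2a and 2b compare a cohort selected for stability with the whole clinic's event rate, which leans toward apparent safety; the clinic rate should be descriptive only, and the Aim 2 comparator should be named

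*Combined protocol and SAP*

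**What the plan says.** The document names two comparators for clinical events and does not say how they relate.

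- **Measures, Safety, items a and b** use the clinic. Item a: "Study participant bleeding events for 12 months prior to enrollment and during the study will be compared to the clinic's bleeding event rate". Item b: "Study participant thromboembolic events for 12 months prior to study enrollment and during the study will be compared to the clinic's thromboembolic event rate".
- **Specific Aims, Aim 2** uses the participants themselves. The hypothesis is that "there will not be a difference between the bleeding and thromboembolic events from baseline (12 months prior to study enrollment") to the yearly event rates at 6, 12 and 24 months.
- **Analysis** follows the second route: "Differences from baseline and at study completion will be compared utilizing McNemar Test for categorical data", with paired tests for other data types. It names no test, margin or decision rule for cohort against clinic.

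The clinic figures are in Procedures, under Safety: "The events rates for 2013 clinic data are listed below, including a 95%CI". They are major bleed 1.88% (1.3-2.62%), serious bleed 0.5% (0.23-0.94%) and thromboembolism 0.22% (0.06-0.6%). No restriction to stable patients is stated. The Background describes a clinic of about 1800 patients that starts therapy, "follows patients on short-term and long-term antithrombotic therapy, manages the transition from inpatient to outpatient care".

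The cohort is much narrower. Participants need indefinite therapy, a 2-3 goal, 12 months in the clinic and a weekly dose stable for 6 months. The exclusions include bleeding or thromboembolism that needed medical intervention in the past 6 months, thrombocytopenia, active liver disease, heavy alcohol use and non-adherence. On two cohorts of stable patients the Background says: "Both studies found that bleeding and thromboembolic events were significantly lower with stable patients compared to the other patients on warfarin".

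**The concern.** On the protocol's own account, patients like these have fewer events than other warfarin patients, so the whole-clinic rate probably exceeds the rate they would have had on usual intervals. Longer intervals could then raise events and leave the cohort at or below the clinic figure. If that result were reported as reassurance, the error would run in the unsafe direction, and the Sample Size section says results may inform larger studies.

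The plan also compares the pre-enrolment year with the clinic rate, which could in principle expose the selection gap. Whether it can depends on how many events that year would hold.

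**Working it through.** **1. Reproduce the clinic figures.** The documents give percentages without counts. Inferred counts of 34, 9 and 4 events in 1808 patients, with exact (Clopper-Pearson) 95% limits, give:

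| Event | Inferred | Reproduced | Stated |
|---|---|---|---|
| Major bleed | 34/1808 | 1.88% (1.31-2.62) | 1.88% (1.3-2.62) |
| Serious bleed | 9/1808 | 0.50% (0.23-0.94) | 0.5% (0.23-0.94) |
| Thromboembolism | 4/1808 | 0.22% (0.06-0.57) | 0.22% (0.06-0.6) |

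This fits a denominator of the whole clinic (about 1800), not a stable subset.

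**2. Expected events at the clinic rate.** The percentages are treated as rates per patient-year. Follow-up is at most 75 × 2 = 150 patient-years (planned enrolment, two years, no dropout).

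- On study: major bleeds 150 × 0.0188 = 2.82; thromboembolism 150 × 0.0022 = 0.33.
- Pre-enrolment year: 75 × 0.0188 = 1.41 and 75 × 0.0022 = 0.17.

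The pre-enrolment year is therefore too sparse to calibrate the selection gap, even before the entry criteria remove events from it.

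**3. What selection would do.** Let f be the usual-interval rate in eligible patients divided by the clinic rate. The documents give no value, so f is varied as an assumption. The cohort only equals the benchmark when its rate has risen by a factor of 1/f. For major bleeds over 150 patient-years, a one-sided 2.5% exact Poisson test against a fixed 1.88% needs 8 events (8/150 = 5.3% per year). The plan sets no such test; it is used here only as a yardstick. The expected count after a true doubling is 2 × f × 2.82.

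| f (assumed) | Rise that only equals the clinic rate | Expected count after a doubling | Chance observed rate is at or below the clinic's (2 events or fewer) | Chance of 8 or more |
|---|---|---|---|---|
| 1 | none | 5.64 | 8% | 21% |
| 0.75 | 1.33-fold | 4.23 | 21% | 7% |
| 0.5 | 2-fold | 2.82 | 46% | 0.8% |
| 0.25 | 4-fold | 1.41 | 83% | under 0.1% |

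For thromboembolism the test needs 3 events. The chance of flagging a doubling is 3% at f = 1 and 0.5% at f = 0.5.

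The f = 1 row shows that sparse events alone make the comparison weak. The lower rows show what the choice of comparator adds.

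**4. The within-patient baseline.** The entry criteria remove events needing intervention from the last 6 of the 12 baseline months. If events fall evenly over time and every major bleed needs intervention (both assumptions), only 6/12 of the expected baseline events can appear. At the clinic rate that is 1.41 × 0.5 = 0.7 major bleeds instead of 1.4. An unchanged underlying rate would then look like a rise of up to twofold. Fatal bleeds, which count as major, also cannot occur in the baseline of someone who enrols.

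The two comparators therefore lean in opposite directions.

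**The case against.** A reader might infer that Aim 2 as a whole is judged against the clinic rate. The documents do not support that. The Aim 2 hypothesis and the named tests use participants' own baseline, and the stopping rule takes its event rates from the cited 4- versus 12-week randomised trial. A data monitoring committee also reviews events, and time in range and extreme INRs are further safety measures.

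Nor can it be said that the clinic comparison favours the longer interval whatever its true effect. A rise larger than 1/f puts the expected rate above the clinic's.

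Three objections concern size:

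- The Background's stable patients had all INRs in range; this study requires a stable dose and allows one adjustment.
- The cited cohorts compared stable with other patients, whereas the clinic rate includes stable patients, which dilutes the contrast.
- Participants' events come from self-report and study record review, which may find more than routine clinic collection and partly offset the bias.

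These objections stand. They prevent any figure for the bias and limit the consequence, but they do not make the clinic rate a like-for-like comparator. The feasibility framing excuses low power. It does not excuse leaving open which of two oppositely biased comparators supports a safety statement.

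**Conclusion.** The point holds for Measures 2a and 2b. The clinic rate is unrestricted, the cohort is selected for stability and no recent event, and the protocol's own Background implies that the benchmark is too high for it. The direction, toward apparent safety, rests on that Background statement carrying over to this cohort and on event ascertainment not reversing it. The size cannot be computed: the twofold masking at f = 0.5 illustrates an assumed ratio and is not an estimate.

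The clinic comparison is a supplementary measure without a named test. The comparison that carries the Aim 2 hypothesis has a bias of its own, toward apparent harm, and the document acknowledges neither bias. With about 2.8 major bleeds expected at most at clinic rates, failure to find a difference on either comparison would be weak evidence of safety.

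**What to change.** 1. In Measures 2a and 2b, state that the all-clinic rate is descriptive context only, is expected to exceed the rate in stable patients, and will not support a conclusion of safety or of no difference.
2. Reconcile those items with Aim 2 and the Analysis section by naming the within-patient comparison as the Aim 2 comparison. State that the six-month event exclusion lowers its baseline.
3. Report on-study event rates per patient-year with exact confidence intervals.

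These changes need only wording and a simple calculation. The study gives up one favourable benchmark.

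Optionally, add a clinic rate restricted to patients who meet the same criteria but stayed on usual intervals, if existing data and approvals allow. This is neither free nor clean. Eligible patients are invited, so those left on usual intervals would be mainly people who declined or were not reached, and following them needs chart work and permission. Precision would also stay poor. If the matched rate were known exactly and f were 0.5 (1.41 major bleeds expected in 150 patient-years), 5 events would be needed, and the chance of flagging a true doubling would be about 16%.

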Follow-up visits will be scheduled following the extended interval protocol, which includes visits at 5-6 weeks (if not already), then 7-8 weeks follow up, and then follow up at 11-12 weeks, if the participant continues to be on a stable dose of warfarin and the INRs are within the goal range of 2-3 (including lab variation) (figure 1). If the participant is already at a 5-6 week follow-up, which is usual care, their next follow-up interval will be 7-8 weeks. Follow-up visits will continue to be scheduled at 11-12 weeks if those criteria are met. If a situation arises where the extended interval is no longer appropriate (e.g. single INR outside of goal range and lab variation, a participant has a procedure requiring interruption of warfarin, drug interaction, hospitalization, etc.), the clinical situation will be managed per usual care (figure 2). If there was a permanent weekly dose adjustment or if the temporary dose change was more than 1 month, the participant would return to usual clinic care. They could requalify for the extended interval protocol when they have been on the same warfarin dose for at least 6 months, except for a single, one-time adjustment. Planned procedures with INR(s) out of range would not exclude a patient. If there was not a permanent weekly dose adjustment or if the temporary

dose change was less than or equal to one month, two therapeutic INRs 4 weeks apart will be needed prior to starting the participant on the extended interval.

If an unexpected INR is drawn, the pharmacist provider will assess the reason why the INR was drawn (figure 3). If it was due to a change in health status, the participant would most likely require shorter follow-up which would meet the criteria for the situation described previously. If it was truly a random INR, the next follow-up should be scheduled for the originally intended interval (e.g. Scheduled for 8 week follow-up and INR was drawn at 6 weeks. Next follow-up scheduled for 8 weeks).

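### Safety measure 2e counts extreme INRs with no denominator or time window, although the intervention itself changes how often INR is tested

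*Combined protocol and SAP*

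**What the plan says.** Under Measures, Safety, item 2e is "Number of extreme INRs (<1.5, ≥4.5". Apart from the two cut-offs, nothing defines it.

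The neighbouring items are more specific. Items 2a and 2b name the 12 months before enrolment and the study period. Item 2c says "Utilization for 12 months prior to study enrollment will be compared to utilization during study enrollment". Item 2d is "Baseline TTR (12 months prior and 6 months prior) for each patient and during study". The first Aim 2 hypothesis puts clinical events on a yearly basis: "bleeding and thromboembolic events from baseline (12 months prior to study enrollment) to events/year at 6, 12, and 24 months".

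The Analysis section has one general sentence on before/after comparison: "Differences from baseline and at study completion will be compared utilizing McNemar Test for categorical data and paired t-test", with the Wilcoxon signed-rank test as the ordinal alternative. It does not mention 2e, number of tests or length of follow-up.

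On testing frequency, the Background says of usual care: "The maximum interval between INRs is currently 5-6 weeks". The Intervention section replaces this with "visits at 5-6 weeks (if not already), then 7-8 weeks follow up, and then follow up at 11-12 weeks", for as long as dose and INR stay stable. Feasibility item 1b, "Change in frequency of appointments from baseline", will show part of this change, but it is not linked to 2e.

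**The concern.** The number of extreme INRs found depends on how often a patient goes out of range and on how often anyone looks. The intervention deliberately changes the second. A raw count cannot separate the two, so it can fall simply because fewer samples were drawn.

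Extreme INRs are a direct laboratory safety signal for less frequent testing. A lower count on the extended schedule could be read as reassurance when it reflects fewer tests. The missing window adds a second distortion: the study lasts two years and the baseline one. Follow-up also varies, because data collection ends at withdrawal of consent or death.

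Putting 2e on the events-per-year basis used in Aim 2 would not cure this, because the yearly count still falls with the yearly number of tests.

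**Working it through.** The plan gives no expected number of extreme INRs, so there is no stated figure to reproduce. The check counts scheduled tests from the plan's own intervals.

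**Inputs**
- Usual care: every 5 or 6 weeks at most (Background).
- Study ladder: 5-6, then 7-8, then 11-12 weeks; a participant already at 5-6 weeks starts at 7-8 (Intervention).
- Windows: 52 weeks of baseline (Aim 2; Measures); 104 weeks of study (Safety, two-year duration).
- Assumptions: no step-backs; the same probability of an extreme value at each test before and during the study.

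**Formula.** Expected count = patients × tests per patient × risk per test. With patients and risk per test held constant, the ratio of expected counts equals the ratio of tests, so no event rate has to be assumed.

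**Baseline, whole tests in 52 weeks.** Every 5 weeks: 52/5 = 10.4, so 10. Every 6 weeks: 52/6 = 8.67, so 8.

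**Study, whole tests.** Lower ends of the ladder are set against 5-weekly care and upper ends against 6-weekly care.

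| Ladder (weeks) | Tests in weeks 1-52 | Tests in weeks 53-104 | Baseline tests |
|---|---|---|---|
| 5, 7, then 11 | 5, 12, 23, 34, 45 (n = 5) | 56, 67, 78, 89, 100 (n = 5) | 10 |
| 7, then 11 | 7, 18, 29, 40, 51 (n = 5) | 62, 73, 84, 95 (n = 4) | 10 |
| 6, 8, then 12 | 6, 14, 26, 38, 50 (n = 5) | 62, 74, 86, 98 (n = 4) | 8 |
| 8, then 12 | 8, 20, 32, 44 (n = 4) | 56, 68, 80, 92, 104 (n = 5) | 8 |

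**Ratio of expected counts, study to baseline, in the order of the table**
- Weeks 1-52: 5/10, 5/10, 5/8, 4/8 = 0.50-0.63.
- Weeks 53-104: 5/10, 4/10, 4/8, 5/8 = 0.40-0.63.
- All 104 study weeks against 52 baseline weeks: 10/10, 9/10, 9/8, 9/8 = 0.90-1.13.
- The 104 weeks annualised: 5/10, 4.5/10, 4.5/8, 4.5/8 = 0.45-0.56.

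Read the other way, at a test ratio of 0.50 the risk per test could double (1/0.50 = 2) with no change in the expected count. At 0.63 it could rise by a factor of about 1.6 (1/0.63).

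**Allowing for step-backs.** The plan does not say how soon an out-of-range INR is rechecked. A simulation assumed 6-weekly usual care, a 2-week recheck, a further test 4 weeks later and then re-extension. It used assumed per-test probabilities of 10-30% for out-of-range and 1-5% for extreme values. The ratio of extreme counts was 0.57-0.70 for 12 against 12 months, and 1.26-1.49 for 24 against 12 months.

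**The case against.** The strongest reply is that 2e never promises a comparison. Read literally it is a tally, and a tally of dangerous values is a legitimate descriptive record. The before/after reading comes from the general sentence in the Analysis section and from the pattern of the other safety items. This stands as a limit: the misreading is a risk, not a stated intention. But even a tally needs its period and number of tests to be interpretable.

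Second, the clean ladder describes patients who stay in range. An INR beyond either cut-off should trigger a step-back, so contributors to 2e are tested more often than the table shows. This also stands. In the simulation the fall over equal windows is smaller but remains. The 24-against-12-month count rises, the opposite of false reassurance. That reinforces the point that the answer depends on an unstated window.

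Third, the upper ratios owe something to rounding. With 8.67 in place of 8 baseline tests, 5/8.67 = 0.58, 9/8.67 = 1.04 and 4.5/8.67 = 0.52. Also, 5-6 weeks is a maximum interval, so 8-10 is roughly a floor for baseline tests. Neither changes the direction over equal windows.

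Fourth, TTR and appointment frequency are reported anyway. They offset the gap only in part: TTR records time in range, not how far out a value is.

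Finally, equal risk per test is an assumption, since risk at 12 weeks may differ from risk at 5 weeks.

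**Conclusion.** The concern holds. As written, 2e moves with testing frequency even if INR control does not. On schedule alone, with equal risk per test, the expected count in the first study year is 0.50-0.63 of baseline. With the simulated rechecks it is 0.57-0.70. Against a 12-month baseline, the 24-month count ranges from about level (0.90-1.13) to higher (1.26-1.49 with those rechecks). The same control can thus look better, unchanged or worse according to the window.

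The defect in the definition is certain. The exact size is not, because the documents do not give the recheck frequency or the risk per test. The consequence is modest: no stopping rule uses 2e, neither Aim 2 hypothesis depends on it, and the study is mainly about feasibility. The change should be made because it is cheap and the measure bears directly on the safety of longer intervals.

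**What to change.** Redefine 2e as extreme INRs (below 1.5, or 4.5 and above) reported in two ways: as a proportion of INRs tested, and per patient-year. Show the number of INRs tested and the patient-time for each period. Compare the 12-month baseline with study months 1-12 and 13-24, and keep the comparison descriptive. Read the per-INR proportion first, because the per-patient-year rate still moves with testing frequency. Keep the plain count in the table so that no dangerous value is dropped.

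State two limits beside the result. Rechecks after an out-of-range INR cluster around excursions, so the per-INR proportion is not free of bias. Selection on six months of stable dosing favours the baseline period.

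Where the chart shows why an INR was drawn, add a sensitivity analysis limited to routinely scheduled tests.

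Cost: the main change needs no new data. INR values and dates are already on the data list, and on-study INRs are needed for TTR, so it means a short definition and one small table. The sensitivity analysis needs the reason for each draw, which is not on the list. That would take some judgement-based chart review, and the analysis can be left out if the reason is not recoverable.
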